1.0 Background

Pleural infection is a condition that requires hospitalization for management and is associated with significant in-hospital morbidity and mortality^[1]. Predictors of poor outcome include advancing age, poor nutrition, hospital-acquired infection and impaired renal function.^[2] Medical management is centred on appropriate antibiotic treatment and fluid drainage usually by the means of an intercostal tube. Up to 30% of patients fail medical treatment and referred for surgery.^[3] A recent systematic review of adults patient with pleural infection has shown that the demographics of patients with pleural infection are different in patients from high-income vs lower income countries; the latter being of younger age and lower comorbidity burden.^[4] However, the results of the review did not show significant differences in patient outcomes. The same systematic review pointed to the need for more data from patients residing in lower income countries given that the majority of data is contributed by studies from higher income countries.^[4]

This study aims to prospectively investigate the incidence of pleural infection in a large tertiary centre gathering demographic and clinical data about patients recruited. In addition, the study will examine the different treatment offered and how this related to in-hospital outcomes (length of hospital stay, rate of referral to surgery and mortality).

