2.1.5 Study assessments

PICS is a strictly observational study and all data gathered will be related to the patient's clinical care. The following data will be collected:

- Average age and gender proportion of patients admitted (from screening log)
- Comorbidities
- RAPID score
- Baseline blood tests and follow up inpatient tests (minimum urea and electrolytes, full blood count, C-reactive protein, and serum albumin)
- Pleural fluid results
- Microbiological results (pleural fluid and blood)
- Ultrasound findings
- CT findings if available
- Baseline and follow up CXRs
- Treatments received for pleural infection
- Length of hospital stay (LOS)
- Outcome at discharge (medical, surgical, dead)

Medical treatment will include: thoracentesis, chest drain, fibrinolytic, medical thoracoscopy

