4.0 Statistics

Continuous variables will be compared between the study arms using t-test or Mann Whitney test according to the normality of the study data. Categorical variables (including primary outcome measure) will be compared using the Chi squared test or Fisher exact test as appropriate.

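### The cohort aim of relating treatments to outcomes is met only by unadjusted tests, and nothing uses the collected RAPID score to adjust that comparison

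*Protocol*

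**What the plan says.** The aim stands in Protocol section 1.0: "the study will examine the different treatment offered and how this related to in-hospital outcomes". The outcomes named there are hospital stay, surgical referral and mortality. The same section gives prognostic factors: "Predictors of poor outcome include advancing age, poor nutrition, hospital-acquired infection and impaired renal function".

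Treatment is not allocated. Section 2.1.2 describes it as standard care, and section 2.1.5 states that "PICS is a strictly observational study". Section 2.1.5 lists the RAPID score, comorbidities and blood tests among the data collected. It names four kinds of medical treatment: thoracentesis, chest drain, fibrinolytic and medical thoracoscopy.

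Section 4.0 consists of two sentences. The first reads "Continuous variables will be compared between the study arms using t-test or Mann Whitney test according to the normality of the study data". The second reads "Categorical variables (including primary outcome measure) will be compared using the Chi squared test or Fisher exact test as appropriate".

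Section 2.1.6 lists the cohort outcomes. Treatments appear there only as a range to be described. A separate item plans to correlate inpatient outcomes with baseline clinical, laboratory and imaging measurements. Section 2.1.2 has inpatient outcomes recorded at discharge or at death, whichever comes first.

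**The concern.** In usual care, the features that predict a poor outcome may also influence which treatment a patient receives. A comparison of treatment groups by t-test, Mann-Whitney, chi-squared or Fisher test then mixes any effect of treatment with the difference in who was treated. The protocol names the predictors and collects a risk score, but section 4.0 gives neither a part in the treatment comparison.

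Length of stay has a further difficulty. If follow-up ends at death and stay is compared by a simple two-sample test, a patient who dies early counts as a short stay. The group with more early deaths then looks better on that outcome.

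At stake is the reading of the cohort results. A crude difference in stay, referral or death could be taken for a treatment effect, in either direction, and the protocol names no method that would separate the two.

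**Working it through.** **1. Which comparison does section 4.0 cover?** The cohort has no arms. The only two-group comparison described is in section 2.2.1: 15 irrigated patients against 15 matched controls. There are two readings.

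- If both sentences of section 4.0 concern the sub-study, the document states no analysis for the cohort aim.
- If they also cover the cohort, its treatment comparisons are unadjusted.

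The sentence on continuous variables mentions arms, so the first reading is the natural one for it. The sentence on categorical variables does not mention arms, and two of the three outcomes in the aim (referral and death) are categorical. The second reading therefore cannot be excluded.

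**2. Is adjustment provided elsewhere?** The correlation item in section 2.1.6 could take RAPID as a predictor of outcome. It does not name RAPID, gives no method, and does not concern the comparison of treatments.

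**3. How large could the case-mix effect be?** The protocol gives no figure to reproduce, so every input in this step is assumed. Take a high-risk share h, mortality mH in high-risk and mL in low-risk patients, and probabilities of treatment pH and pL. Treatment has no effect.

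Risk in treated = [h·pH·mH + (1−h)·pL·mL] / [h·pH + (1−h)·pL]. For the untreated, replace each p by 1−p.

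Example with h = 0.2, mH = 0.20, mL = 0.05, pH = 0.5, pL = 0.2:

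- treated: (0.020 + 0.008)/(0.10 + 0.16) = 0.1077
- untreated: (0.020 + 0.032)/(0.10 + 0.64) = 0.0703
- crude risk ratio: 0.1077/0.0703 = 1.53, where the true ratio is 1

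Over h = 0.2, 0.3, 0.4 and mH = 0.20, 0.30, with mL = 0.05:

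| Who is treated more often | pH, pL | Crude risk ratio |
|---|---|---|
| High-risk patients | 0.5, 0.2 | 1.53 to 1.74 |
| Neither | 0.3, 0.3 | 1.00 |
| Low-risk patients | 0.2, 0.5 | 0.57 to 0.69 |

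A second set of assumptions, again with no treatment effect: mortality 3–5% in low-risk and 15–30% in high-risk patients, and a high-risk share of 30% v 50% or 20% v 60% in two treatment groups. The crude odds ratio is 1.36 to 2.59. An unadjusted test at two-sided 0.05 rejects in 6.5% to 34.5% of studies with 50 per group, and in 9.2% to 60.2% with 100 per group. At the upper end (3% and 30% mortality, 20% v 60% high-risk):

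- group risks: 0.8 × 0.03 + 0.2 × 0.30 = 0.084 and 0.4 × 0.03 + 0.6 × 0.30 = 0.192
- odds ratio: (0.192/0.808)/(0.084/0.916) = 2.59

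**4. Early death counted as a short stay.** Inputs are assumed: mortality 15% v 5%, the same mean stay m in survivors, mean day of death t. Mean recorded stay is m − (mortality)·(m − t), so the groups differ by (0.15 − 0.05)(m − t). With m from 10 to 20 days and t from 3 to 7 days, the range is 0.10 × (10 − 7) = 0.3 to 0.10 × (20 − 3) = 1.7 days. The group with more deaths appears to have the shorter stay.

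**5. Are there enough events to adjust?** The one documented input is in section 1.0: "Up to 30% of patients fail medical treatment and referred for surgery". With an assumed cohort of 50, 100 or 200 patients, that is at most 15, 30 or 60 referrals (0.30 × 50, 0.30 × 100, 0.30 × 200). The protocol gives no mortality figure, so the number of deaths cannot be derived. A single score asks less of the data than entering each predictor separately.

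**The case against.** The strongest reply is that this is largely silence, not error. If section 4.0 is written for the sub-study, it says nothing wrong about the cohort, and the choice of covariates and the handling of death may stand in a SAP that is not shown. The aim is one descriptively worded sentence in the Background, it does not recur among the outcomes in section 2.1.6, and no passage claims causality. Section 2.1.2 fixes when outcomes are recorded, not how stay is analysed, and section 2.1.5 records death as its own category.

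Much of this stands, and it limits the severity. It does not remove the point. The protocol states the aim, then fixes its methods by name, and those methods do not serve the aim on either reading of section 4.0.

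A reader might infer more in three ways, and the documents do not support any of them.

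- That RAPID has no use anywhere in the protocol. The correlation item in section 2.1.6 could include it. What is absent is its use to adjust the treatment comparison.
- That comparisons will suffer time-related bias, because patients must stay long enough to receive a later procedure. This depends on how patients are grouped by treatment, and the protocol does not say.
- That the cohort results will be biased by a known amount or in a known direction. The illustrations fall on both sides of 1 and rest on assumed inputs.

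**Conclusion.** The point holds as a mismatch between a stated cohort aim and the only analysis methods shown. Followed for that aim, section 4.0 gives crude contrasts that may reflect case mix, although a risk score is already being collected. It also leaves open that an early death is analysed as a short stay.

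The figures above show only that material distortion is possible without any treatment effect. They assume that risk influences both treatment and outcome, and the protocol supplies no value for either link. The text does not support calling this a planned treatment-effect analysis: the wording is descriptive and the study is declared observational. Severity is minor to moderate, and the change is a cheap improvement.

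**What to change.** Amend section 4.0 in four respects:

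1. State that the tests between study arms apply to the irrigation sub-study.
2. For the cohort aim, compare outcomes by treatment with adjustment for the RAPID score where event numbers allow.
3. Analyse stay so that an in-hospital death is not counted as a short stay, for example as time to discharge alive with death as a competing event.
4. Report crude contrasts as descriptive associations, not treatment effects. If only description is intended for the whole cohort aim, say so.

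The cost is a few sentences and modest extra analysis, because RAPID, stay and outcome at discharge are already collected. There are limits. Deaths may be too few to adjust mortality. Section 1.0 describes "fluid drainage usually by the means of an intercostal tube", so some treatment contrasts may have little variation. Residual confounding will remain after adjustment for one score, so adjusted results also need cautious wording.

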2.0 Methods

PICS STUDY

2.1.1 Setting

The Pleural Infection Cohort Study (PICS) will aim to recruit consecutive patients admitted to Alexandria University Hospitals with pleural infection during a one-year period from the starting date of the study.

2.1.2 Design

The study will be designed as a modified trial within cohort (TwIC) study.^[5] PICS will primarily aim to recruit patients prospectively to gather clinical and demographic data on patients admitted with pleural infection in addition to clinical data on tests performed and treatments received as part of the standard care. The in-patient outcomes will be recorded at the time of discharge data or death, whichever is earlier. Within the TWIC design, PICS will be a platform for recruiting patients to interventional trials for eligible patients within the cohort (see 'consenting' section)

2.1.3 Eligibility

All adult patients admitted with pleural infection who are willing to sign an informed consent will be recruited. Pleural infection will be defined by the presence of one of the following: a)

the presence of pus in the pleural space; b) positive pleural fluid gram stain or culture; or c) pleural fluid pH < 7.2 or pleural fluid glucose < 40 mg/dL in the setting of acute respiratory infection.

2.1.4 Consenting and co-enrollment

In the TwiC design patients are consented to take part in the cohort study with the possibility of being randomized in the future into trials without being specifically told if a given eligible participant is randomized into a control arm of a trial^[5].

The consenting process for PICS will involve obtaining consent for the core observational part of the study. There will be a separate clause asking for permission to enroll a participant into an interventional trial if the participant meets the eligibility criteria. Participants will have the opportunity to accept taking part in PICS and reject taking part in interventional trials. The consent form will be modified to include clauses for any new trial anchored to the PICS platform. Participants will be given clear written information about PICS and any additional trials and will be given enough time consider taking part.

All consenting eligible participants for an interventional trial will be informed in case they are randomized to a given trial regardless of the arm they are randomized to. In all cases, a single participant will not be enrolled into more than one interventional trial at the same time.

2.1.5 Study assessments

PICS is a strictly observational study and all data gathered will be related to the patient's clinical care. The following data will be collected:

- Average age and gender proportion of patients admitted (from screening log)
- Comorbidities
- RAPID score
- Baseline blood tests and follow up inpatient tests (minimum urea and electrolytes, full blood count, C-reactive protein, and serum albumin)
- Pleural fluid results
- Microbiological results (pleural fluid and blood)
- Ultrasound findings
- CT findings if available
- Baseline and follow up CXRs
- Treatments received for pleural infection
- Length of hospital stay (LOS)
- Outcome at discharge (medical, surgical, dead)

Medical treatment will include: thoracentesis, chest drain, fibrinolytic, medical thoracoscopy

2.1.6 Outcomes

- Examining the incidence of pleural infection admissions locally, the demographics of this cohort and range of medical treatments offered.
- Correlating inpatient outcomes with baseline clinical, biochemical, microbiological and radiological parameters

- Percent of eligible patients randomized to interventional trials

'Antiseptic irrigation for patients with pleural infection' sub-study

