2.2.1 Rationale and design

The antiseptic povidone-iodine can safely be instilled into the pleural for the purpose of pleurodesis^[6]. Pleural irrigation with antiseptics is used in adults with open drainage for chronic empyema^[7] and has been described in the acute management of paediatric pleural infection^[8].

This sub-study will investigate the safety and usefulness of povidone-iodine pleural irrigation in 15 eligible patients recruited to PICS. A matched control group will be used and will be composed of 15 patients previously recruited to PICS without receiving povidone-iodine pleural irrigation.

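### The only sub-study described randomises nobody, so it adds nothing to the percent-randomised outcome, and its matched earlier controls need not meet the entry conditions that irrigated patients must meet

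*Protocol*

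**What the plan says.** Protocol 2.1.2 gives the framework: "The study will be designed as a modified trial within cohort (TwIC) study", and "PICS will be a platform for recruiting patients to interventional trials for eligible patients within the cohort". Section 2.1.4 explains that cohort members consent "with the possibility of being randomized in the future into trials". Through a separate clause they may join PICS and decline interventional trials. Those who accept "will be informed in case they are randomized to a given trial regardless of the arm they are randomized to". Section 2.1.6 then lists as a cohort outcome "Percent of eligible patients randomized to interventional trials".

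One intervention is described. Section 2.2.1 plans "povidone-iodine pleural irrigation in 15 eligible patients recruited to PICS". For the comparison, "A matched control group will be used and will be composed of 15 patients previously recruited to PICS", with the further condition that they were not irrigated. The matching variables are not named.

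Section 2.2.2 adds entry criteria: a unilocular collection, no known or suspected thyroid disease, no iodine allergy, and no large collection persisting on imaging at 24-48 (no unit is printed; presumably hours) after the tube goes in that is judged to need a further drainage procedure. Section 2.2.3 puts the first irrigation at 24 to 72 hours from tube insertion. The efficacy outcomes in 2.2.4 include length of stay, additional aspirations or tubes, and failure of medical treatment. Section 4.0 plans two-sample t or Mann-Whitney tests and chi-squared or Fisher tests, with no adjustment.

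**The concern.** Two things do not fit together.

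First, the platform sections and the 2.1.6 outcome presuppose random allocation, while the one intervention described allocates nobody at random. A reader of the final report could not tell from that outcome how well the platform recruited to irrigation, because irrigated patients do not count in it.

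Second, the two groups do not enter on the same terms. An irrigated patient has accepted the trial clause, is still being drained at 24 to 72 hours, and has been shown by then not to have a large undrained collection needing another procedure. As 2.2.1 is worded, a control only has to be an earlier, unirrigated, matched PICS patient. Patients whose first drain did badly can therefore be controls but cannot be irrigated. At stake is an apparent benefit on length of stay, extra tubes or treatment failure that comes from who was let in.

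**Working it through.** **Step 1: the outcome in 2.1.6.** The measure is (patients randomised) / E, where E is the number eligible. The protocol does not give E. In 2.2.1 the 15 controls were recruited before the irrigated patients they are compared with, so they cannot have been randomised against them. No random selection of the irrigated 15 is described either. The sub-study's numerator is 0, and 0/E = 0% for any E.

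If the outcome counted enrolment instead, with the 15 irrigated patients as the numerator, it would be informative. Over an assumed range of E:

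| E (assumed) | Percent randomised, as written | Percent enrolled, 15/E |
|---|---|---|
| 30 | 0% | 50% |
| 40 | 0% | 37.5% |
| 60 | 0% | 25% |
| 100 | 0% | 15% |

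**Step 2: entry conditions side by side.**

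| Condition | Irrigated 15 | Control 15 |
|---|---|---|
| Accepted the trial clause (2.1.4) | Yes | Not required |
| Meets 2.2.2, including no large residual collection needing another procedure | Yes | Not required |
| Still drained at 24 to 72 hours (2.2.3) | Yes, by construction | Not required |
| Recruited | Not stated | Earlier |
| Matched | n/a | Yes, variables not named |

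The second row bears directly on an outcome. A control with a large residual collection who then has another drainage procedure counts as needing an additional aspiration or tube. Each such control adds 1/15 = 6.7 percentage points to the control rate; two add 13.3 and three add 20. The irrigated group has been screened free of these cases. The same patients would be expected to stay longer and to fail medical treatment more often. The number of such controls is unknown.

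**Step 3: what an imbalance would do to a test (illustration only).** The protocol states no alpha, power or effect size, so it has no figure to reproduce. Assume a two-sided 5% t-test, n = 15 per group, no treatment effect and a residual group shift of d standard deviations. The noncentrality is d × √(15/2) = 2.739d, with 28 degrees of freedom and critical value 2.048.

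| d (assumed) | Noncentrality | Chance of p < 0.05 |
|---|---|---|
| 0 | 0 | 5.0% |
| 0.1 | 0.274 | 5.8% |
| 0.2 | 0.548 | 8.3% |
| 0.3 | 0.822 | 12.5% |
| 0.4 | 1.095 | 18.5% |
| 0.5 | 1.369 | 26.2% |

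No value of d is supported by the protocol. Here d is what remains after matching.

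**The case against.** The 2.1.6 outcome belongs to the platform, not to irrigation. It speaks of trials in the plural; 2.1.4 provides for new trials to be attached, and section 3.0 allows for more than one. A reader might infer that the outcome is fixed at 0% by design. That does not follow, and this objection stands: the protocol shows only that the one sub-study described contributes nothing.

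The trial-within-cohort label is applied to PICS as a whole. Irrigation is openly called a sub-study with matched controls, and 2.1.4 tells participants about randomisation only if it happens. That also stands, so the protocol does not expressly mislabel the sub-study. The word *modified* in 2.1.2 does not close the gap, however, because the departure spelled out in 2.1.4 is disclosure of randomised arms, which still assumes randomisation.

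The controls are matched and come from the same prospective cohort, in one hospital group within one planned year. This limits calendar drift and some imbalance. The matching variables may be set in a statistical analysis plan that is not shown, and one could read 2.2.2 as covering both groups. But 2.2.1 attaches eligibility only to the irrigated 15. Matching on baseline characteristics would not by itself remove a difference in early response to drainage or in trial consent.

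The safety outcome, adverse events within 24 hours of first irrigation, does not depend on the controls. That stands; the problem is confined to efficacy.

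Finally, a small non-randomised study is a legitimate choice. A reader might infer that the sub-study must be randomised. The protocol does not support that: randomising needs about 30 eligible consenting patients instead of 15, and no accrual figure shows that this is feasible.

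**Conclusion.** The point holds in a limited form. The only sub-study described adds 0 to the percent-randomised outcome, whatever E is, unless a randomised trial is later attached under 2.1.4.

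The stronger defect is the control rule. As worded, controls may include patients whom 2.2.2 would exclude and patients who declined trials. Through the residual-collection criterion and the unadjusted tests, this favours irrigation on length of stay, additional tubes and treatment failure. The conclusion rests on reading 2.2.1 as it stands. It falls away if the matching rule already imposes the 2.2.2 criteria at the same time point.

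The direction is clear for the residual-collection criterion. Other differences, such as controls whose tube came out before 24 to 72 hours, could pull the other way on time to tube removal and length of stay. That is a further reason for a common time origin.

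The size is not known. The range of about 6% to 26% for imbalances of 0.1 to 0.5 SD illustrates how sensitive a 15-versus-15 comparison is. It does not measure the bias in this study.

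**What to change.** 1. In 2.1.6, restate the outcome as *percent of eligible patients enrolled in interventional sub-studies*, and report the percent randomised only for any randomised trial added later. Call the irrigation sub-study a non-randomised comparison with matched earlier cohort controls. This is wording only.

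2. In 2.2.1, restrict controls to earlier PICS patients who accepted the trial clause and met all 2.2.2 criteria, assessed at the same point after tube insertion as the irrigated patients. Count time to defervescence, time to tube removal and length of stay from one common origin in both groups. The cost is a smaller control pool and some loss of matching flexibility.

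Controls can remain earlier patients. Insisting on the same calendar period would contradict 2.2.1. Eligible, consenting patients left untreated in that period would probably be few, or selected by whatever prevented treatment.

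The sponsor may instead choose to randomise 1:1, 15 and 15, using the consent and notification steps already in 2.1.4. The total stays at 30, but about 30 eligible consenting patients would be needed within the year. That is a design trade-off, not a condition of putting this point right.
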